# 9.2 Peripheral blood analysis for gene expression, tryptophan metabolism and cytokine abundance

Additional blood samples will be collected at 1st pre-operative treatment, day of surgery, C1D1, and at each adjuvant treatment imaging visits (i.e. every 2 cycles or 8 weeks):

- a) 8m (2x4ml) blood in two 5ml EDTA (purple top) tubes: PBMCs will be isolated, separated and analyzed to generate a gene expression profile.
- b) 10ml blood in one 10ml red top tube: Serum will be analyzed 1) via HPLC for tryptophan and downstream catabolites, as well as for 2) cytokines via an array-based platform.

Responders and non-responders (if separable) will be identified based on progression free- and/or

overall-survival and cross-referenced with gene expression/tryptophan catabolite/cytokine analysis.

Samples will be picked up by laboratory personnel and sent to: [name] laboratory. [name] Lab [contact]; Office [contact]

Please refer to laboratory manual for further details on collection, shipping, processing and storage.

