## 1.5.1 Exploratory Studies

For patients who progress on trial and remain surgical candidates, tissue post treatment with Tremelimumab or MEDI4736 or the combination will be analyzed and compared to the prior specimen.

Additional exploratory studies will include assessment of:

- 1) Profile peripheral blood lymphocytes (PBL)
- 2) Tumor-infiltrating lymphocytes (TIL) throughout treatment.

3) Serum for tryptophan and downstream catabolites, as well as for cytokines.

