#### 10.3 Sample Size, Accrual and Data Analyses Plans

There will be three groups of patients, one group on each agent alone and one group treated with the combination agent. There will be 10 patients per group for a total of 30 patients. These 30 patients must be evaluable for the primary endpoint, meaning that they must have undergone surgery and their blood and tissue samples are available at both the pre- and post-surgery times. In order to attain 10 evaluable patients in each arm, a total of 45 patients will be accrued to the study. Sample sizes of 10 per group allow for the estimation of the proportion of responders in evaluable patients to be within 31% of its true value with 95% confidence. Mean change will be compared between arms. Using standard deviations of change, a sample size of 10 per group will allow the detection of differences of 1.25 standard deviations between groups with 80% power assuming a two-tailed test and a Type I error rate of 5%.

Immunologic measures will be summarized over the three or more time points (pre-treatment, following first treatment/pre-surgery, post-surgery) and changes in these measures will be assessed using repeated measures analysis of variance or Cochran's Q, followed by the paired t-test or the signed rank test for pairwise comparisons using Bonferroni corrections. Safety of the agents alone or in combination will be assessed by summarizing the frequency of adverse events by type, timing, grade and attribution. Response criteria will be based on RANO (including upcoming Immunologic RANO criteria) but since all patients will be post-surgery, the degree, if any, of

residual disease will vary. A patient is evaluable for efficacy if they have undergone at least one follow-up MRI after adjuvant therapy. Immunologic changes will be correlated with MRIs in a descriptive fashion. The secondary endpoint of progression-free survival as well as overall survival will be analyzed using Kaplan-Meier curves. Immunologic changes of T-cells and PDL1 levels will be correlated to survival outcomes using Cox regression analysis. MRI changes will be summarized using means or proportions and statistically analyzed using the signed rank test.

**Performance Status:** Patients will be graded according to Karnofsky Performance Status (KPS)(see appendix C).

**Evaluation of toxicity.** All patients will be evaluable for toxicity from the time of their first treatment as per NCI CTCAE version 4.03

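### Section 9.2 relates the gene-expression, tryptophan and cytokine markers to outcome through an undefined responder split on survival, which loses power against the Cox regression that 10.3 already uses

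*Combined protocol and SAP*

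**What the plan says.** Section 9.2 describes two additional blood samples. From one, "PBMCs will be isolated, separated and analyzed to generate a gene expression profile". The other provides serum for tryptophan and its catabolites and for "cytokines via an array-based platform". The number of genes or analytes is not given.

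The link to outcome is a single sentence: "Responders and non-responders (if separable) will be identified based on progression free- and/or" "overall-survival and cross-referenced with gene expression/tryptophan catabolite/cytokine analysis". It names no cut-off, landmark time, rule for choosing between the two endpoints, statistical test or multiplicity method, and it does not say what makes groups separable.

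Section 10.3 handles other markers differently: "Immunologic changes of T-cells and PDL1 levels will be correlated to survival outcomes using Cox regression analysis". Cox regression is named there only for those two marker sets, and Bonferroni correction only for pairwise comparisons of the immunologic measures. On size, "There will be 10 patients per group for a total of 30 patients".

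Section 1.5.1 introduces its list with "Additional exploratory studies will include assessment of", and the list includes "Serum for tryptophan and downstream catabolites, as well as for cytokines".

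**The concern.** PFS and OS are times, and some of them will be censored: 10.3 censors patients at last follow-up, and 4.6 does not require patients who enter another trial to be followed for survival or progression. Reducing such an outcome to two groups has two costs.

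- It treats everyone on the same side of the cut as alike, so the ordering of event times within each group is lost.
- A patient censored before the cut belongs to neither group, and the plan has no rule for that patient. Cox regression uses the follow-up that was observed.

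The open choices (PFS, OS or both; where to cut; whether to cut at all) raise a second, conditional concern. If any of them were settled after the marker results had been seen, chance associations would be favoured.

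At stake is the quality of the leads from about 30 patients: real correlates missed, or false ones carried into later work.

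**Working it through.** **The plan's own figures.** Section 9.2 states no sample size, alpha or power, so it has no figure to reproduce. The figures in 10.3 belong to other quantities, and they do reproduce:

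- Precision of a proportion with n = 10: 1.96 × √(0.25/10) = 0.310, the stated 31%.
- Power for 1.25 SD with 10 per group, normal approximation: Φ(1.25 × √(10/2) − 1.96) = Φ(0.835) = 79.8%, the stated 80%.

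**Inputs for the check.** From 10.3: n = 30 evaluable patients. Assumed, because the documents give no values: one normally distributed marker; exponential PFS with a median of 3 months; OS equal to PFS plus an exponential time with a median of 5 months; no censoring; hazard ratio per SD of the marker between 1.5 and 2.0.

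**Tests compared**, each two-sided at 5%:

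- Split: patients are grouped on survival time and the marker means compared by pooled t-test (30 − 2 = 28 df).
- Cox: score test on the continuous marker, z = U/√V, where U sums, over events, the marker value minus its risk-set mean, and V sums the risk-set variances.

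**Power for PFS, n = 30**

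| HR per SD | Median split | Cox | Difference (points) |
|---|---|---|---|
| 1.5 | 30% | 51% | 21 |
| 1.75 | 48% | 75% | 27 |
| 1.8 | 50–52% | 78–80% | about 28 |
| 2.0 | 64–66% | 88–90% | about 24 |

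Ranges reflect separate simulation runs. At HR 1.8, cutting at the largest gap in survival time instead of at the median gives 49%. For OS the median split has 53%, 77% and 90% power against 77%, 95% and 99% for Cox at HR 1.5, 1.75 and 2.0. OS figures are higher because the marker was made to act both before and after progression.

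The Cox score test is slightly liberal at this size (5.6% against 5.0% for the median split), so a small part of the gap is due to its higher error rate.

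**False positives per marker under no effect, n = 30, 5% test**

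| How the split is chosen | Rate |
|---|---|
| Fixed median split | 5.0% |
| Largest gap in survival time | 4.8–4.9% |
| PFS or OS, whichever separates more on survival | 4.9% |
| Best two-cluster split of log PFS (5,000 runs) | 5.4% |
| Better marker p-value of the median PFS and median OS splits | 9.5% |
| Best marker p-value of three PFS cuts | 11.7% |
| Best marker p-value over all cuts from the 20th to 80th percentile, PFS | 26.5% |
| The same, PFS or OS | 43.7% |

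The first four rows choose the groups without using the marker. Under no effect the marker is independent of survival, so the rate stays at about 5%; the simulation error on 5.4% is √(0.05 × 0.95/5,000) = 0.3 points. The last four rows choose using the marker's own p-value.

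**Number of markers.** Any per-marker test also needs multiplicity control. With m independent true nulls each tested at 5%, the chance of at least one false positive is 1 − 0.95^m: 40% for m = 10, 64% for 20, 92% for 50 and 99% for 100. These counts are assumed.

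**The case against.** The strongest reply is that 9.2 does not describe a search for the cut that makes a marker significant. Read plainly, patients are separated on survival first and the assays are looked at afterwards. A reader might infer from the open wording that the plan builds in a false-positive rate of 26% to 44%. The documents do not support that: those figures require the cut or endpoint to be tuned to each marker's result. This part of the reply stands, and the inflation is a worst case that the text leaves possible.

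It is also fair that 9.2 sets no alpha and makes no confirmatory claim, that 1.5.1 lists the serum work as exploratory, and that no sample size depends on it. This limits the weight of the point. It does not justify a weaker method when a better one is already in the plan.

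Two further inferences go too far. One is that the same blood draws are analysed in two ways. The blood visits in 9.1 and 9.2 coincide, but PD-L1 is read on archival tumour slides (9.3) and part of the T-cell work uses resected tissue (9.1). The other is that the two methods are incompatible. A group display can sit beside a Cox model, and 9.2 does not exclude one. What remains is that different methods are named for the same kind of outcome, and the one named in 9.2 is the weaker.

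Finally, the power simulations have no censoring, so the censoring problem is argued but not measured.

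**Conclusion.** The point holds as a loss of power and a missing definition in an exploratory analysis. With 30 patients, a median split gives up roughly 21 to 28 percentage points of power for PFS across hazard ratios of 1.5 to 2.0 per SD. Censored patients have no place in the split. Error inflation is conditional: near 5% if the groups are formed on survival alone, at worst about 26% (PFS) or 44% (PFS or OS) per marker if the choice follows the marker result.

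The sizes rest on assumed medians, hazard ratios, a normally distributed marker and no censoring. The direction of the power comparison does not depend on the exact values tried. The primary endpoint and its sample size are unaffected.

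**What to change.** Replace the responder sentence in 9.2 with text such as:

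> Baseline values and early changes of the gene-expression, tryptophan-catabolite and cytokine measures are related to PFS and OS as continuous covariates in Cox models as in 10.3. Models using change to the pre-surgery or C1D1 sample start follow-up at that sample (landmark), and false-discovery-rate control is applied within each assay family. Any responder grouping is for display only, on one endpoint and landmark fixed before marker data are examined.

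The landmark is needed because 10.3 starts both clocks at first treatment, while the pre-surgery sample comes about 14 days later and C1D1 about 14 + 14 = 28 days later. A patient must remain event-free to that sample to enter the model, so counting the earlier time would build in immortal-time bias. The false-discovery-rate step is needed because Cox regression alone does nothing about the number of analytes.

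Cost: a change of analysis text and a little more analysis work, with no new samples or visits. Patients with an event before the landmark drop out of the change models, though they stay in the baseline models.

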#### 9.3 Archival Tissue for PD- L1 analysis

Four unstained slides cut at  $5\mu$  from a representative tumor block will be delivered to the [name] lab for PD-L1 analysis (see section 9.1 for contact information).

An additional 3 unstained slides cut at 5 microns will be hand delivered to PCF IHC within 7 days of sectioning for commercial analysis of PD-L1. We will use the commercially available assay [e.g. Ventana Medical Systems, Inc. (Ventana)].

Please refer to laboratory manual for further details on collection, shipping, processing and storage.

### 10.0 STATISTICAL CONSIDERATIONS

#### 10.1 Study Design/Study Endpoints

To determine the T-cell changes that occur in recurrent GBM treated with Tremelimumab and MEDI4736 as single agents and in combination.

- To evaluate the safety of either Tremelimumab or MEDI4736 alone and in combination in patients with recurrent GBM.
- To determine the time to progression for patients treated with either Tremelimumab or MEDI4736 alone and in combination of both post-surgery.
- To determine the overall survival for patients treated with Tremelimumab or MEDI4736 alone and in combination of both post-surgery.
- To correlate T-cell changes and PDL1 expression with patients outcome.
- To assess MRI changes in patients treated with either Tremelimumab, or MEDI4736 alone, and in combination of both post-surgery.

#### 10.3 Sample Size, Accrual and Data Analyses Plans

There will be three groups of patients, one group on each agent alone and one group treated with the combination agent. There will be 10 patients per group for a total of 30 patients. These 30 patients must be evaluable for the primary endpoint, meaning that they must have undergone surgery and their blood and tissue samples are available at both the pre- and post-surgery times. In order to attain 10 evaluable patients in each arm, a total of 45 patients will be accrued to the study. Sample sizes of 10 per group allow for the estimation of the proportion of responders in evaluable patients to be within 31% of its true value with 95% confidence. Mean change will be compared between arms. Using standard deviations of change, a sample size of 10 per group will allow the detection of differences of 1.25 standard deviations between groups with 80% power assuming a two-tailed test and a Type I error rate of 5%.

Immunologic measures will be summarized over the three or more time points (pre-treatment, following first treatment/pre-surgery, post-surgery) and changes in these measures will be assessed using repeated measures analysis of variance or Cochran's Q, followed by the paired t-test or the signed rank test for pairwise comparisons using Bonferroni corrections. Safety of the agents alone or in combination will be assessed by summarizing the frequency of adverse events by type, timing, grade and attribution. Response criteria will be based on RANO (including upcoming Immunologic RANO criteria) but since all patients will be post-surgery, the degree, if any, of

residual disease will vary. A patient is evaluable for efficacy if they have undergone at least one follow-up MRI after adjuvant therapy. Immunologic changes will be correlated with MRIs in a descriptive fashion. The secondary endpoint of progression-free survival as well as overall survival will be analyzed using Kaplan-Meier curves. Immunologic changes of T-cells and PDL1 levels will be correlated to survival outcomes using Cox regression analysis. MRI changes will be summarized using means or proportions and statistically analyzed using the signed rank test.

**Performance Status:** Patients will be graded according to Karnofsky Performance Status (KPS)(see appendix C).

**Evaluation of toxicity.** All patients will be evaluable for toxicity from the time of their first treatment as per NCI CTCAE version 4.03

**Time to Progression:** From date of first treatment to the date of first observation of definitive progressive disease, non-reversible neurologic progression or increasing steroid requirements (applies to stable disease only), death due to any cause, or early discontinuation of treatment. Patients not reaching the progression endpoint at last follow-up will be censored at that time.

**Time to Death**: From date of first treatment to date of death due to any cause. Patients alive at last follow-up will be censored at that time.

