## 2.0 OBJECTIVES & ENDPOINTS

## 2.1 Primary Objective & Endpoints

To determine the T-cell changes that occur in recurrent GBM treated with Tremelimumab and MEDI4736 as single agents and in combination. The changes from baseline will be assessed in blood samples and tissue samples before treatment and post-surgery for all patients in the 3 arms. A comparison between the changes observed in the 3 arms will be made.

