# 6.0 ENDPOINT ASSESSMENT

## 6.1 **Primary Endpoint**

To determine the T-cell changes (immunologic changes) that occur in recurrent GBM treated with Tremelimumab and MEDI4736 as single agents and in combination. The changes from baseline will be assessed in blood samples and tissue samples before treatment and post-surgery for all patients in the 3 arms. A comparison between the changes observed in the 3 arms will be made.

Only patients who have had pre-treatment blood sampling, have undergone surgery with pre-surgical blood sampling, and are able to continue to post-operative drug treatment with blood sampling prior to the first post-surgical dose will be evaluable for this endpoint.

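### The randomised between-arm part of the primary endpoint has no named test, baseline covariate or contrast adjustment; t-based power is 75 to 77%, and baseline ANCOVA would often, but not always, recover it

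*Combined protocol and SAP*

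**What the plan says.** Section 2.1, repeated in 6.1, closes the primary endpoint with the statement that "A comparison between the changes observed in the 3 arms will be made". Patients are randomised in equal numbers (section 4.1), so this is the randomised contrast of the trial.

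Section 10.3 and the Study Summary cover that contrast in one clause, "Mean change will be compared between arms". The sizing is on the SD scale of the change score: "a sample size of 10 per group will allow the detection of differences of 1.25 standard deviations between groups". The claimed power is 80%, two-sided at the 5% level. A separate basis for 10 per arm is that a responder proportion can be estimated "within 31% of its true value with 95% confidence".

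The tests that are named for immunologic measures are repeated measures ANOVA or Cochran's Q over the time points, "followed by the paired t-test or the signed rank test for pairwise comparisons using Bonferroni corrections". No baseline covariate appears anywhere.

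Section 6.1 limits evaluability for the primary endpoint: "Only patients who have had pre-treatment blood sampling, have undergone surgery with pre-surgical blood sampling", together with "blood sampling prior to the first post-surgical dose". Section 9.1 makes the blood drawn before the first dose the baseline sample.

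**The concern.** The paired t-test, the signed rank test and Cochran's Q all work within patients over time; none can contrast independent arms. Repeated measures ANOVA could, but no arm term is stated. The Bonferroni clause belongs to the paired follow-up tests, and nothing is said about the three arm contrasts. The randomised comparison therefore has a power statement but no test, and its form could be chosen after the data are seen.

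Three things follow. The stated 80% may not hold for the test eventually used. Three contrasts, each at 5%, carry roughly a 12% chance of at least one false positive per measure. And a baseline blood value available for every evaluable patient is not used for precision, in a trial with 10 patients per arm.

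**Working it through.** **Inputs from section 10.3:** n = 10 evaluable per arm, difference d = 1.25 SD of change, two-sided α = 0.05, stated power 80%. **Assumed, because the documents do not give them:** the pre-post correlation r, and k = post-treatment SD divided by pre-treatment SD.

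**1. Reproduce the plan's figure.** Noncentrality = d√(n/2) = 1.25 × √5 = 2.795. Normal approximation: Φ(2.795 − 1.960) = Φ(0.835) = 79.8%. This is the stated 80%, for one pair of arms, unadjusted.

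**2. Use a t-test on change.** With the same noncentrality in the noncentral t distribution:

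| Error term | α = 0.05 | α = 0.05/3 = 0.0167 |
|---|---|---|
| Normal approximation | 79.8% | 65.6% |
| Two arms, 18 df | 75.3% | 57.1% |
| Three arms pooled, 27 df | 76.9% | 60.0% |

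On 27 df, the difference detectable with 80% power is 1.30 SD at 0.05 and 1.53 SD at 0.0167.

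**3. Familywise error.** Three pooled-error contrasts at 0.05, under no difference between any arms, give 11.9% from the studentized range distribution (simulation: 11.7%).

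**4. Add the pre-treatment value as covariate.** With pre-treatment variance set to 1:

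- Change-score variance: 1 + k² − 2rk.
- ANCOVA residual variance: k²(1 − r²).
- Ratio R = k²(1 − r²)/(1 + k² − 2rk), which is (1 + r)/2 when k = 1.

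The raw difference is held at 1.25 SD of change. ANCOVA noncentrality is 2.795/√[R(1 + F/27)] on 26 df, averaged over F with 1 and 27 df; this term carries chance baseline imbalance. Power against 76.9% (α = 0.05) or 60.0% (α = 0.0167) for change scores:

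| k | r | R | α = 0.05 | α = 0.0167 |
|---|---|---|---|---|
| 1 | 0.3 | 0.65 | 90.5% | 79.3% |
| 1 | 0.5 | 0.75 | 86.1% | 72.5% |
| 1 | 0.7 | 0.85 | 81.7% | 66.1% |
| 1 | 0.9 | 0.95 | 77.3% | 60.5% |
| 1 | 0.95 | 0.975 | 76.2% | 59.1% |
| 1.5 | 0.3 | 0.87 | 80.7% | 64.9% |
| 1.5 | 0.5 | 0.96 | 76.7% | 59.7% |
| 1.5 | 0.7 | 1.00 | 75.3% | 58.0% |
| 2 | 0.3 | 0.96 | 76.9% | 60.0% |
| 2 | 0.5 | 1.00 | 75.2% | 57.8% |

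**5. Bound the loss.** 1 + k² − 2rk − k²(1 − r²) = (1 − rk)², which is never negative, so R never exceeds 1. The worst case is rk = 1, where ANCOVA pays only for one df and chance imbalance: 75.2% against 76.9%, a loss of 1.7 points at α = 0.05.

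**6. Would an arm term in the repeated measures ANOVA help?** With complete pre and post data, the ordinary arm-by-time contrast is the change-score difference. In one simulated data set of 3 × 10 both were 0.766 (SE 0.393), so that route alone adds no precision.

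**The case against.** The strongest reply is that nothing here is biased. Under randomisation, comparing mean change is unbiased; it matches the objective as worded, and the power statement uses the same scale. A reader might infer that the planned comparison is invalid. The documents do not support that, and the absence of adjustment is itself read from silence, since no test is named.

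A second tempting inference is that ANCOVA raises power whenever the correlation is low to moderate. It does not: at k = 1.5 and r = 0.5 there is no gain, and at k = 2 and r = 0.5 there is a small loss. Section 8.2.3 describes tremelimumab as enhancing T-cell activation and expansion, so equal variances before and after treatment cannot be presumed. This part of the objection stands and limits the claim.

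It is also fair that the t-versus-normal gap and the multiplicity do not come from omitting a covariate, and that ANCOVA cures neither. With equal variances, power at α = 0.0167 stays below 80% at r = 0.3 and above. Nor does the gain reach the whole endpoint: fresh tissue is taken only at surgery, and binary responder measures need another test.

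The objection does not remove the gap in the text. The plan quotes 80% power and a 5% error rate for a contrast without saying how it will be tested.

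**Conclusion.** The point stands in limited form. Section 10.3 and the Study Summary name no between-arm test, baseline covariate or adjustment for the three arm contrasts, although the contrast is part of the primary endpoint. That rests on the text alone. The stated 80% is a normal approximation; a t-based comparison of change gives 75 to 77% at 5% and 57 to 60% at 1.67%.

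The case for ANCOVA is conditional. With equal variances it adds about 14, 9 and 5 points at r = 0.3, 0.5 and 0.7. It adds about nothing near r = 0.9, or when post-treatment SD is 1.5 to 2 times baseline at moderate r; the largest loss is about 1.7 points. These figures assume approximate normality and a common slope. With a possible gain much larger than the possible loss, and the covariate already collected, it is a reasonable default for continuous blood measures.

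A reader might also infer that 10 per arm must be increased. This point does not support that: n = 10 has its own precision basis (1.96 × √(0.25/10) = 0.31), which is unaffected.

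**What to change.** In section 10.3 and the Study Summary:

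- **Continuous blood T-cell measures:** compare arms by ANCOVA with arm as factor and the pre-treatment value as covariate. Name the time point in advance: the day-of-surgery sample, the sample before the first post-surgical dose, or both. If a mixed model is preferred, constrain the arms to a common pre-treatment mean. Fix any rank or permutation version beforehand.
- **Arm contrasts:** adjust the three by Holm or Bonferroni.
- **Binary responder measures:** compare arms with a test for independent proportions.
- **Tissue measures:** compare arms without baseline adjustment where no comparable pre-treatment value exists. State the rule for any measure with a baseline from archival tumour, which section 5.1 requests for all patients.
- **Within-arm change over time:** keep repeated measures ANOVA, Cochran's Q and the paired tests for this purpose.
- **Power sentence:** restate it for the named test and alpha, giving the assumed correlation and variance ratio.

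The cost is a few sentences, one error df (27 to 26) and a common-slope assumption. No new blood samples and no change in sample size are needed. Multiplicity across the several T-cell measures in section 9.1 remains to be settled separately.

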## **3.0 PATIENT ELIGIBILITY**

The target population for this study is patients with recurrent glioblastoma. This will be a single-center trial conducted at neuro-oncology clinic of Northwestern University.

A total of 30 evaluable subjects will be needed for this trial. The accrual cap is 45 patients, in order to cover those patients that do not make it to the first evaluable time point. Hence, the total accrual per arm will be up to 15. Approximately 4 potentially eligible patients are seen per month, and it is anticipated that at least 2 per month will be accrued. Potential patients may be referred to the Principal Investigator (PI) at Northwestern University, [name], at [contact].

Eligibility will be evaluated by the study team according to the following criteria. Eligibility waivers are not permitted. Subjects must meet all of the inclusion and none of the exclusion criteria to be registered to the study. Study treatment may not begin until a subject is registered.

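### The stated 80% power at 1.25 SD with 10 per arm holds only if the SD is known and for one unadjusted pair of arms; a two-sample t-test gives 75%, and reaches 80% at 1.32 SD

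*Combined protocol and SAP*

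**What the plan says.** The primary endpoint in Section 6.1 (also Section 2.1) is the change in T-cell measures, and part of it is between arms: "A comparison between the changes observed in the 3 arms will be made". Section 10.3 repeats this as "Mean change will be compared between arms" and fixes the size: "There will be 10 patients per group for a total of 30 patients". It then claims that "a sample size of 10 per group will allow the detection of differences of 1.25 standard deviations between groups with 80% power", for a two-tailed test with 5% Type I error. The Sample Size entry of the Study Summary makes the same claim.

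No formula is given for the power figure, and no test is named for the between-arm comparison. The only multiplicity wording in Section 10.3 comes in the next paragraph, on measures summarised over time points. There, repeated measures ANOVA or Cochran's Q is "followed by the paired t-test or the signed rank test for pairwise comparisons using Bonferroni corrections".

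**The concern.** This is the only power statement for the between-arm part of the primary endpoint, and it is questionable in two ways.

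- **Estimated SD.** The effect is expressed in SD units and no SD of change is assumed anywhere, so the SD has to come from the trial data. With 10 patients per arm, a formula that treats the SD as known overstates power noticeably.
- **Unstated scope.** Three arms make three pairs. The sentence does not say whether its 5% applies to one pair or to all three.

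A non-significant arm comparison would be read against a benchmark that the design does not meet, and a reader could take the 5% as covering the whole three-arm comparison.

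**Working it through.** **Inputs (Section 10.3).** n = 10 evaluable per arm; difference d = 1.25 SD; two-sided α = 0.05; target power 80%.

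**1. Reproduce the plan's figure (SD known, normal formula).**

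- Detectable difference = (z₀.₉₇₅ + z₀.₈₀) × √(2/n) = (1.960 + 0.842) × √0.2 = 2.802 × 0.4472 = 1.253 SD.
- Noncentrality at d = 1.25: 1.25 × √(10/2) = 2.795. Power = Φ(2.795 − 1.960) = Φ(0.835) = 79.8%.

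This matches the stated 1.25 SD and 80%. The neighbouring precision claim of 31% is also a large-sample normal figure: 1.96 × √(0.25/10) = 0.310.

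**2. Estimate the SD (t-test).** The noncentrality stays at 2.795, but the critical value rises from 1.960 to the t quantile and the power comes from the noncentral t distribution.

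| One pair of arms, two-sided 5%, n = 10 per arm | Critical value | Power at 1.25 SD | Difference with 80% power |
|---|---|---|---|
| Normal, SD known | 1.960 | 79.8% | 1.253 SD |
| Two-sample t, 18 df | 2.101 | 75.3% | 1.325 SD |
| t with SD pooled over three arms, 27 df | 2.052 | 76.9% | 1.300 SD |

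**3. Other readings of the sentence.** A one-sided t-test gives 85.1%, but the plan says two-tailed. A one-sample or paired t-test with n = 10 gives 93.9%, but the claim is about differences between groups. A three-arm 5% F-test gives 78.5% if two arms are equal and the third differs by 1.25 SD, and 65.4% if the third arm lies midway. No two-sided between-group test that estimates the SD reaches 80%.

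**4. Evaluable patients needed to keep 1.25 SD (single pair).** With 11 per arm, power is 79.6% (81.0% with the SD pooled over three arms); with 12 per arm it is 83.3%.

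**5. Scope across the three pairs.** Three unadjusted two-sample t-tests have a family-wise error of about 12% when all arms are equal (simulation, 200,000 runs). If the 5% were held across the three pairs, power for one 1.25 SD pair with 10 per arm would depend on the method:

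| Method (none is specified in the plan for arm pairs) | Power at 1.25 SD | Difference with 80% power |
|---|---|---|
| 5% F-test, then unadjusted pairs; third arm equal to one of the two | 71% (simulation) | not computed |
| Same; third arm midway | 64% (simulation) | not computed |
| Tukey, 27 df (critical t 2.479) | 63% | 1.50 SD |
| Bonferroni, α = 0.05/3, 18 df | 57% | 1.57 SD |
| Bonferroni, α = 0.05/3, 27 df | 60% | 1.53 SD |

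**6. Does the Bonferroni wording already cover this?** No. It is attached to the paired t-test and the signed rank test, which compare time points within the same patients. Neither can compare independent randomised arms.

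**The case against.** The strongest reply is that nothing was miscalculated. The figure is right under a normal approximation, which is a common planning shortcut, and that formula is inferred from a numerical match because the plan names none. The two-sample t-test is not named either. With the SD pooled over three arms the shortfall is only about 3 points and the shift about 0.05 SD. The effect size is generic and tied to no marker. Accrual also gives some room: "the total accrual per arm will be up to 15", and one or two evaluable patients above 10 would bring single-pair power to about 80% or more. Finally, this is a small mechanistic phase II trial that does not commit to three confirmatory pairwise tests, so arm-pair multiplicity is partly a matter of choice.

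Much of this is fair. The fault is an undisclosed approximation, optimistic at this size, not a slip within its own formula. The shortfall from estimating the SD is modest, and adjusting for arm pairs is the sponsor's decision. Three points remain:

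- The pooled analysis also misses 80%.
- The extra accrual is an allowance to reach 10 evaluable patients, and the claim is made for 10.
- Even without any adjustment, the text should say that its 5% is for one pair.

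**Conclusion.** The concern holds. For 10 evaluable patients per arm and a two-sided 5% test between two arms, power at 1.25 SD is 75.3% with the two-sample t-test, or 76.9% with the SD pooled over three arms; 80% is reached at 1.32 or 1.30 SD respectively. The overstatement is about 5 points (about 3 with pooling), or 0.05 to 0.07 SD in the detectable difference. These figures assume roughly normal changes with equal SD in each arm, and that mean change is compared by a t-type test.

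The scope gap is separate. The stated figure applies to one pair at the full 5%, and the text does not say so. The adjusted powers of 57% to 71% apply only if the sponsor decides to hold 5% across the three pairs. This should be fixed, but it calls for a correction of wording and does not undermine the design.

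**What to change.** Name the between-arm test in Section 10.3, then restate the power there and in the Study Summary to match it. For the two-sample t-test:

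> With 10 evaluable patients per arm, a single two-sided 5% two-sample t-test between one pair of arms has 75% power for a difference of 1.25 SD and 80% power for 1.32 SD. No adjustment is made for the three arm pairs.

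If the arms will instead be compared with the SD pooled over all three, give 77% and 1.30 SD. If the sponsor chooses to hold 5% across the three pairs, name the method and give its power, for example Tukey (63% at 1.25 SD, 80% at 1.50 SD) or Bonferroni with separate t-tests (57% at 1.25 SD, 80% at 1.57 SD). State also that the existing Bonferroni wording refers to time points.

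The cost is a sentence or so in two places and a slightly less favourable figure. No patients are added. If 12 or more of the up to 15 patients accrued per arm prove evaluable, single-pair power at 1.25 SD will exceed 80%, but the plan should not rely on this.
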